3.4.2 Inclusion Criteria

Subjects are required to meet the following inclusion criteria in [Table 3.4.2-1](#).

Table 3.4.2-1 Inclusion Criteria	
1.	Male and female subjects aged ≥ 18 years with confirmed diagnosis of ADPKD (during participation in prior tolvaptan trials) who have 
 • Completed and transferred from the double-blind Trial 156-13-210 (12-month period including post-treatment follow-up, regardless of whether this was on-treatment or off-treatment), or • Completed Trial 156-08-271 or a prior tolvaptan trial, or • Interrupted or discontinued treatment in a tolvaptan trial other than Trial 156-13-210. Subjects may be enrolled with the medical monitor approval, and additional close monitoring may be required at the beginning of the trial • Renal function will be assessed during screening by using historical laboratory values (in the last 3 months) for serum creatinine levels to calculate the eGFR. The eGFR values will be estimated based on the CKD-EPI formula. (Levey AS et al. Ann Intern Med. 2009; 150:604–612)
2.	Estimated glomerular filtration rate ≥ 20 mL/min/1.73 m ² (calculated using the CKD-EPI formula) within 3 months prior to the baseline visit. Subjects who have an eGFR ≤ 20 mL/min/1.73 m ² may be permitted to enter the trial with medical monitor and sponsor approval and increased frequency of monitoring to ensure safety of subjects.

eGFR=estimated glomerular filtration rate; CKD-EPI= Chronic Kidney Disease - Epidemiology

Protocol 156-13-211

3.4.3 Exclusion Criteria

Subjects will be excluded if they meet any of the exclusion criteria in [Table 3.4.3-1](#).

1.	WOCBP who do not agree to practice 2 different methods of birth control or remain abstinent during the trial and for 30 days after the last dose of IMP. If employing birth control, 2 of the following precautions must be used: vasectomy of partner, tubal ligation, vaginal diaphragm, intrauterine device, birth control pill, birth control implant, birth control depot injection, condom, or sponge with spermicide.
2.	Women who are breast-feeding and/or who have a positive pregnancy test result prior to receiving IMP.
3.	Need for chronic diuretic use.
4.	Hepatic impairment based on liver function abnormalities other than that expected for ADPKD with cystic liver disease during screening based on recent historical laboratory values (in the last 3 months).
5.	Subjects with contraindications to required trial assessments (contraindications to optional assessments, eg, MRI are not a limitation).
6.	Subjects who, in the opinion of the investigator or medical monitor, have a medical history or medical finding inconsistent with safety or trial compliance. This includes prior evidence of significant hepatic injury deemed to be related to tolvaptan use.

WOCBP=women of childbearing potential; IMP=investigational medicinal product

Non-childbearing potential in women is defined as female subjects who are surgically sterile (ie, have undergone bilateral oophorectomy or hysterectomy) or female subjects who have been postmenopausal for at least 12 consecutive months.

Subjects may be rescreened, at the discretion of the medical monitor, if the exclusion characteristic has changed or resolved. In the event that a subject is rescreened, a new ICF must be signed and a new screening number assigned and screening procedures repeated.

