3.7 Trial Procedures

Trial assessment time points are summarized in [Table 3.7-1](#).

Protocol 156-13-211

Table 3.7-1 Schedule of Assessments							
	Screening (-30 to -1 days prior to Baseline)^a	Baseline/ Day 0	Monthly^b (± 7 days)	Every 3 months^b (± 14 days)	Early Termination/End of Treatment (+ 7 days)	Titration Contact (phone contact)	Follow-up 7 days post- treatment (+ 7 days)
Informed consent	X						
Inclusion/Exclusion	X	X					
Demographics, Medical/ADPKD history ^c	X						
Dietary review	X	X	X	X	X		
CCI							
Vital signs ^d	X	X	X	X	X		X
Chemistry Blood Samples^e							
Serum Chemistry Panel	X ^f				X		
Liver Function tests ^g	X		X	X	X		X
Sodium	X		X	X	X		
Creatinine	X		X	X	X		X
Hematology and coagulation	X				X		
Urinalysis	X		X	X	X		
Urine osmolality^h	X		X	X	X		
Urine specific gravity	X		X	X	X		
Urine pregnancy test (WOCBP only) ⁱ	X		X	X	X		X
Urine at-home pregnancy test kits dispensed ^j		X	X	X			
Physical examination ^k	X	X	X	X	X		
Tolerability/Dosing Review		X	X	X	X	X	
Interactive Response Technology Entry	X	X	X	X	X	X ^l	X
Drug dispensation		X	X	X		X ^l	
Drug reconciliation			X	X	X	X ^l	
CCI							

Protocol 156-13-211

	Screening (-30 to -1 days prior to Baseline) ^a	Baseline/ Day 0	Monthly ^b (± 7 days)	Every 3 months ^b (± 14 days)	Early Termination/End of Treatment (+ 7 days)	Titration Contact (phone contact)	Follow-up 7 days post- treatment (+ 7 days)
Adverse events	X ⁿ	←-----→					
Concomitant medications ^o		←-----→					

^aThe last visit assessments from the previous trial can be combined with the screening and baseline visits for this trial, with all required assessments from each visit performed only once.

^bMonthly visits are for subjects < 18 months on tolvaptan, and every 3 month visits are for subjects > 18 months on tolvaptan

^cIncludes prior trial identifiers (screening identification [ID], subject ID, site ID, prior tolvaptan ADPKD trial protocol number).

^dVital signs at each visit include seated heart rate, calibrated blood pressure and post void body weight. Height should be performed only at screening.

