ⁱA urine pregnancy test for pregnancy for women of childbearing potential (WOCBP) will be performed at screening, at every 3 months visits, at the End of Treatment (EoTx) visit, and at the follow-up visit. On suspicion of pregnancy, an unscheduled urine or serum pregnancy testing will be performed. Positive urine pregnancy tests should be confirmed with a serum pregnancy test.

^jAt-home urine pregnancy test kits will be dispensed to WOCBP to be used if a menstrual period is missed between visits. Kits will be dispensed as needed throughout the trial.

^kA full physical examination is required at screening. At other visits, an optional “directed” physical examination may be performed to focus on PKD-related signs and symptoms.

Protocol 156-13-211

^lIf during the titration contact the determination is made to adjust the dose regimen, dose adjustments will be made using dispensed supply, and dose instructions will be provided by the investigator. The subject's current dose will be entered into the interactive response technology (IRT) at each visit. Drug dispensation/reconciliation will be conducted on a monthly basis for subjects who have monthly trial visits and once every 3 months for subjects who have trial visits every 3 months. If additional drug supply is required for titration purposes, the site will arrange a subject visit for dispensation.

CCI

ⁿAt screening, AEs reported as ongoing or resolved at the end of the prior trial will be assessed to determine entry as either medical history or ongoing event for this trial.

^oOnly concomitant medications ongoing at the baseline visit and throughout the trial will be recorded. This would occur at the screening visit only if the screening visit occurs simultaneously with the last visit from a previous tolvaptan trial.

Protocol 156-13-211

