3.7.1 Schedule of Assessments

3.7.1.1 Screening (-30 days to 1 day prior to Baseline)

Screening for eligibility is required for all subjects. The screening and baseline visit may be combined with the last visit from either Trials 156-08-271 or 156-13-210 with all required assessments from each visit performed only once. Therefore, in some cases, if a subject enrolls in this trial from a prior tolvaptan trial, the end of trial or last follow-up visit for that trial and the screening and baseline visit for this one may occur simultaneously. Required assessments for the screening visit are as follows:

1. Obtain subject consent.
2. Obtain subject's new screening identification (ID) assigned by interactive response technology (IRT).
3. Determine subject eligibility through inclusion/exclusion criteria
4. Record demographic information and prior trial identifiers (screening ID, subject ID, site ID, prior tolvaptan ADPKD trial protocol number).
5. Record medical/ADPKD history using prior trial data.
6. Review dietary recommendations and compliance
7. Record vital signs (post-void weight and seated heart rate) and in-clinic calibrated blood pressure (BP) measurement. Record height.
8. Collect blood for serum chemistry, liver function panel (ALT, AST, BT, bilirubin [direct], and alkaline phosphatase), serum sodium, serum creatinine, and hematology and coagulation. Hepatitis testing is optional. If hepatitis testing is performed, then both pre- and post-counseling activities relating to hepatitis testing are to be carried out based on local requirements and best practices.
9. Collect urine for urinalysis, urine osmolality (optional), and urine specific gravity.
10. Perform urine pregnancy test on women of childbearing potential (WOCBP). If positive, a follow-up serum test will be performed.
11. Conduct full physical examination.
12. Enter subject into interactive response technology (IRT) including prior trial identifier/information (protocol number, subject ID), confirmed dose regimen, and scheduled date of next visit.
13. Assess AEs reported as ongoing or resolved from prior trial to determine entry as medical history or ongoing event for this trial.
14. Record ongoing concomitant medications. (This will happen only if the screening visit occurs simultaneously with the last visit from a previous tolvaptan trial).

Protocol 156-13-211

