3. CCI [REDACTED]
4. Record vital signs (post-void weight, seated heart rate, and calibrated blood pressure measurement).
5. Dispense at-home urine pregnancy test kits to WOCBP to be used if a menstrual period is missed before the next visit.
6. An optional directed physical examination may be performed to focus on PKD-related signs and symptoms.
7. Assess tolerability/dosing review of investigational medicinal product (IMP).
8. Enroll subject into trial through IRT and obtain IMP.
9. Dispense IMP (sufficient for 1 month or 3 months of dosing based on the subject's required visit schedule for hepatic evaluation as either monthly or every 3 months).
10. Provide subject with dosing instructions to begin on the following day.
11. Record ongoing concomitant medications
12. Assess AEs.

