5.4 Pregnancy

Women of childbearing potential who are sexually active must use an effective method of birth control during the course of the trial and for 30 days after the last dose of IMP in a manner such that risk of failure is minimized. Unless the subject is sterile (ie, women who have had a bilateral oophorectomy and/or hysterectomy or have been postmenopausal for at least 12 consecutive months or remains abstinent, 2 of the following precautions must be used: vasectomy, tubal ligation, intrauterine device, birth control pills, birth control depot injection, birth control implant, condom or occlusive cap (diaphragm or cervical/vault caps) with spermicide. Any single method of birth control, including vasectomy and tubal ligation, may fail, leading to pregnancy.

Before enrolling WOCBP in this clinical trial, investigators must review guidelines about trial participation for WOCBP. The topics should generally include:

- General information
- ICF
- Pregnancy prevention information
- Drug interactions with hormonal contraceptives.
- Contraceptives in current use.
- Guidelines for the follow-up of a reported pregnancy.

Prior to trial enrollment, WOCBP must be advised of the importance of avoiding pregnancy during trial participation and the potential risk factors for an unintentional pregnancy. The subject must sign an ICF stating that the above-mentioned risk factors and the consequences were discussed with her.

During the trial, all WOCBP should be instructed to contact the investigator immediately if they suspect they might be pregnant (eg, missed or late menstrual cycle).

If a subject or investigator suspects that the subject may be pregnant prior to IMP administration, the IMP administration must be withheld until the results of serum pregnancy tests are available. If the pregnancy is confirmed, the subject must not receive the IMP and must not be enrolled in the trial. If pregnancy is suspected while the subject is taking IMP, the IMP must be withheld immediately (if reasonable, taking into consideration any potential withdrawal risks) until the result of the pregnancy is known. If pregnancy is confirmed, the IMP will be interrupted or withheld in an appropriate manner (eg, dose tapering if necessary for subject safety) and the subject will continue to be monitored for the duration of the remainder of the trial or of their pregnancy.

Protocol 156-13-211

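### No pregnancy test is scheduled at Baseline, so with separate visits the last scheduled test can be 30 days old at dispensing and 31 days old at first dose

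*Protocol*

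**What the plan says.** Section 3.4.3, exclusion criterion 2, excludes "Women who are breast-feeding and/or who have a positive pregnancy test result prior to receiving IMP". It does not say how recent the test must be.

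In Table 3.7-1 the row that begins "Urine pregnancy test (WOCBP only" is marked at Screening and blank at Baseline/Day 0. Footnote i says that the test "will be performed at screening, at every 3 months visits, at the End of Treatment (EoTx) visit, and at the follow-up visit". Baseline is not in that list.

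The heading of Section 3.7.1.1 gives the window: "Screening (-30 days to 1 day prior to Baseline". A positive urine test at Screening is followed by a serum test.

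Section 3.7.1.2 (Baseline, Day 0) has the site review the eligibility criteria again (step 1), enrol the subject through IRT and obtain drug (step 8), dispense it (step 9), and then "Provide subject with dosing instructions to begin on the following day" (step 10). The only pregnancy-related step that can be read there is step 5: "Dispense at-home urine pregnancy test kits to WOCBP to be used if a menstrual period is missed before the next visit". Step 3 is redacted, but the table row and footnote i are legible and both leave Baseline out.

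Two rules depend on suspicion. Footnote i adds: "On suspicion of pregnancy, an unscheduled urine or serum pregnancy testing will be performed". Section 5.4 states: "If a subject or investigator suspects that the subject may be pregnant prior to IMP administration, the IMP administration must be withheld", and the hold lasts until serum results are available.

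The UK version of the protocol has the same schedule.

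**The concern.** The second eligibility review takes place on the day the drug is handed over. If Screening was an earlier visit, the site repeats its check of criterion 2 with no new scheduled result. A woman could test negative at Screening, conceive before Day 1, have no reason to suspect it, and start tolvaptan without any deviation from the protocol.

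The protocol treats that outcome as serious. Section 5.4 says a woman with a confirmed pregnancy before dosing must neither receive the drug nor be enrolled. Section 5.1 makes any pregnancy an immediately reportable event that requires the drug to be stopped. What is at stake is fetal exposure that a simple test on the dispensing day could prevent in some cases.

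**Working it through.** The protocol states no figure for the age of the test, so there is nothing to reproduce. The check is day arithmetic.

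**Inputs**
- Screening test: Day -30 to Day -1 (Table 3.7-1; Section 3.7.1.1).
- Dispensing: Day 0 (Section 3.7.1.2, step 9).
- First dose: Day 1 (Section 3.7.1.2, step 10; Table 3.2-1 also starts treatment at Day 1).
- No scheduled test between Screening and Day 1 (Table 3.7-1; footnote i; Section 3.7.1.2).

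**Formula:** age of test = day of event minus day of test.

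| Situation | At dispensing (Day 0) | At first dose (Day 1) |
|---|---|---|
| Separate visits, Screening on Day -30 | 0 - (-30) = 30 days | 1 - (-30) = 31 days |
| Separate visits, Screening on Day -1 | 0 - (-1) = 1 day | 1 - (-1) = 2 days |
| Screening and Baseline combined | 0 days | 1 day |
| Test added at Baseline | 0 days | 1 day |

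**Do the other safeguards cover the interval?**
- *Unscheduled testing and withholding of drug* (footnote i; Section 5.4) start only when someone suspects pregnancy.
- *Home kits* are first handed out at Baseline, and their stated use is for a period missed before the following visit. A subject does not receive one from this trial between Screening and Baseline.
- *Two contraceptive methods or abstinence* (exclusion criterion 1) lower the chance of conception but detect nothing. Section 5.4 itself accepts that a single method can fail.

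**When is the next scheduled test?** The table marks the Monthly column, but footnote i and step 8 of Section 3.7.1.3 set testing every 3 months. On the 3-monthly reading, consecutive scheduled tests could be about 90 - (-30) = 120 days apart (before visit windows), spanning the start of dosing.

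**Who can have separate visits?** Section 3.7.1.1 offers the combined visit to subjects from Trials 156-08-271 and 156-13-210. Subjects from other tolvaptan trials are also eligible (Section 3.4.2). Section 3.1 requires the full screening and baseline assessments for anyone more than 3 months past the preceding trial. The number of women of childbearing potential in these groups is not given.

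**The case against.** The case for leaving the schedule alone has five parts.

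1. *No rule is broken.* Criterion 2 has no recency limit, and a screening test plus a second review of the criteria is a complete procedure. This stands: the point is a gap in the design, not an inconsistency.
2. *The protocol already guards against pregnancy.* It has the two-method or abstinence rule, counselling before enrolment, the instruction to report a missed or late period at once, and withholding on suspicion. These reduce the risk, but none finds a pregnancy that nobody suspects.
3. *Thirty-one days is not the length of undetected risk.* If cycles are of ordinary length (an assumption; the documents say nothing on this), a conception soon after a Day -30 test would often show as a late period near Day 0 and set off the suspicion rules. A conception just before Day 0 would be negative on a Baseline urine test too. The gain is confined to pregnancies that urine can detect but that are not yet suspected. This stands, and it limits the benefit.
4. *During treatment the protocol accepts 3-monthly tests.* A gap of up to 31 days is shorter. But in that phase subjects already hold home kits. Before the first dose they have not yet been given one, and exposure can still be avoided altogether.
5. *A schedule change needs an amendment and ethics approval, at approximately 220 sites.* True, but this applies to any protocol change and is not a disadvantage of this one in particular.

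**Conclusion.** The concern holds. With separate visits, the last scheduled pregnancy test is 1 to 30 days old at dispensing and 2 to 31 days old at first dose. A pregnancy that arises in that interval and is not suspected would not be detected before dosing. Where Screening and Baseline fall on the same day there is no gap.

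The day counts follow directly from the protocol and need no outside assumption. They describe the age of the test, not the number of exposed pregnancies. That number cannot be estimated from the documents, because neither the count of women with separate visits nor a conception rate under the contraception rule is given. It may well be small. The change should be made because it improves subject safety at little cost, not because the present text contradicts itself.

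**What to change.** Add a urine pregnancy test for women of childbearing potential at Baseline whenever Screening took place on an earlier day:

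- mark the Baseline cell of the pregnancy-test row in Table 3.7-1;
- add Baseline to the list in footnote i;
- add a step to Section 3.7.1.2 before step 8, so that the result is known before drug is assigned;
- if the result is positive, carry out the serum test already specified for Screening and do not dispense.

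When Screening and Baseline are combined, one test serves both. Make the same edits in the UK version.

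The cost is one urine kit per woman with separate visits, at an existing visit where kits are already handed out, plus the amendment itself. No extra visit or staff is needed. The age of the last scheduled test at first dose falls from as much as 31 days to 1 day. A very recent conception could still be missed.

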3.5 Trial Endpoints

3.5.1 Safety Endpoints

This trial will have no formal endpoints. Safety variables will be summarized by descriptive statistics, (eg, proportion, mean, median, standard deviation [SD], minimum, and maximum values). In general, summary statistics, including changes from baseline, will be provided for safety variables based on all available data. Safety endpoints will be as follows:

- Adverse events
- Vital signs

Protocol 156-13-211

- Clinical laboratory assessments
- Serum transaminase elevations for frequency (2x, 3x, 5x and 10x ULN), time to onset, time to peak levels, time of offset (< 3x, 2x, or 1x ULN), response to de-challenge and re-challenge and frequency of progression to Hy’s laboratory criteria (ALT or AST > 3x ULN and bilirubin, total (BT), > 2x ULN without alkaline phosphatase ≥ 2x ULN)
- Serum sodium excursions above 145, 150, or 155 mmol/L or below 135, 130, or 125 mmol/L

CCI [REDACTED]

[REDACTED]

[REDACTED]

CCI [REDACTED]

[REDACTED]

[REDACTED]

[REDACTED]

[REDACTED]

[REDACTED]

[REDACTED]

[REDACTED]

[REDACTED]

3.6 Measures to Minimize/Avoid Bias

This is an open-label trial. For subjects entering from placebo-controlled trials, prior therapy (placebo or tolvaptan), will not be known (by trial site, investigator, or sponsor) at the time of entry into this trial.

All blood and urine chemistry will be analyzed and reported by a central laboratory.

3.7 Trial Procedures

Trial assessment time points are summarized in [Table 3.7-1](#).

Protocol 156-13-211

Table 3.7-1 Schedule of Assessments							
	Screening (-30 to -1 days prior to Baseline)^a	Baseline/ Day 0	Monthly^b (± 7 days)	Every 3 months^b (± 14 days)	Early Termination/End of Treatment (+ 7 days)	Titration Contact (phone contact)	Follow-up 7 days post- treatment (+ 7 days)
Informed consent	X						
Inclusion/Exclusion	X	X					
Demographics, Medical/ADPKD history ^c	X						
Dietary review	X	X	X	X	X		
CCI							
Vital signs ^d	X	X	X	X	X		X
Chemistry Blood Samples^e							
Serum Chemistry Panel	X ^f				X		
Liver Function tests ^g	X		X	X	X		X
Sodium	X		X	X	X		
Creatinine	X		X	X	X		X
Hematology and coagulation	X				X		
Urinalysis	X		X	X	X		
Urine osmolality^h	X		X	X	X		
Urine specific gravity	X		X	X	X		
Urine pregnancy test (WOCBP only) ⁱ	X		X	X	X		X
Urine at-home pregnancy test kits dispensed ^j		X	X	X			
Physical examination ^k	X	X	X	X	X		
Tolerability/Dosing Review		X	X	X	X	X	
Interactive Response Technology Entry	X	X	X	X	X	X ^l	X
Drug dispensation		X	X	X		X ^l	
Drug reconciliation			X	X	X	X ^l	
CCI							

Protocol 156-13-211

	Screening (-30 to -1 days prior to Baseline) ^a	Baseline/ Day 0	Monthly ^b (± 7 days)	Every 3 months ^b (± 14 days)	Early Termination/End of Treatment (+ 7 days)	Titration Contact (phone contact)	Follow-up 7 days post- treatment (+ 7 days)
Adverse events	X ⁿ	←-----→					
Concomitant medications ^o		←-----→					

^aThe last visit assessments from the previous trial can be combined with the screening and baseline visits for this trial, with all required assessments from each visit performed only once.

^bMonthly visits are for subjects < 18 months on tolvaptan, and every 3 month visits are for subjects > 18 months on tolvaptan

^cIncludes prior trial identifiers (screening identification [ID], subject ID, site ID, prior tolvaptan ADPKD trial protocol number).

^dVital signs at each visit include seated heart rate, calibrated blood pressure and post void body weight. Height should be performed only at screening.

^eCentral laboratory non-fasting serum laboratory tests will be performed. All subjects must be monitored for hepatic safety monthly until they have known tolvaptan exposure data of at least 18 months. After that, and following the approval of the medical monitor, hepatic monitoring will take place every 3 months. Trial 156-13-210 subjects who are eligible for this trial will have trial visits/hepatic monitoring monthly for the first 18 months of this trial then every 3 months thereafter, because their tolvaptan exposure will be unknown. Once unblinding occurs, it can be determined which subjects received tolvaptan in Trial 156-13-210. These subjects may have their trial visits/hepatic transaminase monitoring changed to every 3 months sooner as their previous tolvaptan exposure in Trial 156-13-210 can count towards the 18 month threshold. Subjects who enroll from other ADPKD tolvaptan trials will be monitored for hepatic safely monthly for their first 18 months they are in this trial.

^fHepatitis testing at screening will be optional. If hepatitis testing is performed, then both pre- and post-counseling activities relating to hepatitis testing are to be carried out based on local requirements and best practices. Upon request, if clinically indicated and approved by the medical monitor, subjects may have the following evaluations in addition to the protocol-specified chemistry panel: serum calcium, phosphorous, parathyroid hormone, vitamin D, and bicarbonate levels.

^gA full liver function panel (AST, ALT, alkaline phosphatase, BT) will be done at screening. All other liver function tests at subsequent visits are for ALT only, unless otherwise clinically indicated. An ALT elevation > 2 × ULN should trigger prompt testing of hepatic function within 72 hours. Any transaminase or bilirubin values which exceed 2 × ULN should prompt immediate retesting within 72 hours. While values remain in an abnormal range, testing frequency should be increased to at least weekly for the first month, gradually returning to monthly, and every 3 months as indicated by the results. Local liver function panel analyses will also be performed more frequently, if necessary.

^hUrine osmolality is optional.

ⁱA urine pregnancy test for pregnancy for women of childbearing potential (WOCBP) will be performed at screening, at every 3 months visits, at the End of Treatment (EoTx) visit, and at the follow-up visit. On suspicion of pregnancy, an unscheduled urine or serum pregnancy testing will be performed. Positive urine pregnancy tests should be confirmed with a serum pregnancy test.

^jAt-home urine pregnancy test kits will be dispensed to WOCBP to be used if a menstrual period is missed between visits. Kits will be dispensed as needed throughout the trial.

^kA full physical examination is required at screening. At other visits, an optional “directed” physical examination may be performed to focus on PKD-related signs and symptoms.

Protocol 156-13-211

^lIf during the titration contact the determination is made to adjust the dose regimen, dose adjustments will be made using dispensed supply, and dose instructions will be provided by the investigator. The subject's current dose will be entered into the interactive response technology (IRT) at each visit. Drug dispensation/reconciliation will be conducted on a monthly basis for subjects who have monthly trial visits and once every 3 months for subjects who have trial visits every 3 months. If additional drug supply is required for titration purposes, the site will arrange a subject visit for dispensation.

CCI

ⁿAt screening, AEs reported as ongoing or resolved at the end of the prior trial will be assessed to determine entry as either medical history or ongoing event for this trial.

^oOnly concomitant medications ongoing at the baseline visit and throughout the trial will be recorded. This would occur at the screening visit only if the screening visit occurs simultaneously with the last visit from a previous tolvaptan trial.

Protocol 156-13-211

